6.3.2.1.3 Guidelines for the treatment of alpelisib induced hyperglycemia

Alpelisib, like other PI3K inhibitors, may affect glucose homeostasis which could result in increases of plasma glucose and insulin resistance (Busaidy 2012). Alpelisib induced hyperglycemia is generally manageable with adequate antidiabetic treatment. Alpelisib induced hyperglycemia typically occurs within the first month of treatment. Patients with pre-diabetes (i.e. FG 100 – 125 mg/dl; 5.6 - 6.9 mmol/L) and those with an established diagnosis of type 2 diabetes mellitus should be monitored carefully, thus allowing an early detection and prompt management of increases in fasting glucose while on alpelisib treatment. However all patients, even those with fasting glucose within normal limits at screening, may develop alpelisib induced hyperglycemia which is an on-target effect seen with PI3K inhibitors. Patients should always be instructed to follow dietary guidelines provided by the American Diabetes Association and/or the European Association for the study of Diabetes, e.g. exercise and dietary advice (e.g. controlled carbohydrate intake, high fiber, low process food intake. Three macronutrient balanced meals and 2 optional small snacks rather than one large meal)'.

Hyperglycemic hyperosmolar non-ketotic syndrome (HHNKS) and diabetic ketoacidosis (DKA) are two of the most serious metabolic complications associated with hyperglycemia. DKA is characterized by ketoacidosis and a comparatively lower hyperglycemic level (blood glucose 250 mg/dL-600 mg/dL), while HHNKS is characterized by more severe hyperglycemia (blood glucose > 600 mg/dL) together with hyperosmolarity and dehydration without significant ketoacidosis. HHNKS is also known as non-ketotic hyperosmolar syndrome, hyperosmolar hyperglycemic state or hyperglycemic hyperosmolar non-ketotic coma. Most patients with HHNKS have a known history of diabetes mellitus Type 2. HHNKS usually develops over a course of many days to weeks, unlike DKA which can develop over the course of a few hours or days.

Detailed guidelines for management of alpelisib induced hyperglycemia is provided in Table 6-3. This includes early administration of metformin or a sodium-glucose cotransporter 2 (SGLT2) inhibitor (alone or in combination with metformin). For more details on metformin XR, please refer to Table 6-3.

Local standard clinical practice may be followed for monitoring and managing hyperglycemia. Fasting glucose will be performed locally for rapid availability for safety evaluation and management guidance. However, it is strongly recommended that dose reduction be based on FPG only.

Special attention should be paid to the risk of hypoglycemia in patients interrupting alpelisib treatment and concomitantly receiving insulin and/or sulfonylureas. Due to the short half-life of alpelisib, all glucose lowering medications should be discontinued when alpelisib is stopped.

If metformin or an anti-diabetic agent is interrupted for radiologic assessments or another reason, then alternative hyperglycemia management should be considered for those days to ensure optimal hyperglycemia management.

Consultation with a diabetologist is highly recommended for better assessment and management of alpelisib-induced hyperglycemia.

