	 If FPG does not resolve to ≤ Grade 1 within 21 days after institution of appropriate anti-diabetic treatment, reduce alpelisib by 1 dose level
	 Continue with anti-diabetic treatment and check fasting glucose levels at least weekly for 8 weeks, then continue checking at least every 2 weeks,

Worst toxicity – CTCAE Grade (value)	Dose Modifications for alpelisib
	alert treating physician if FG > 250 mg/dL (8.9 mmol/L) .
Grade 3	Omit alpelisib and confirm fasting status of the assessment. If non-fasting, re-check within 24 hours.
FG > 250 - 500 mg/dL [> 13.9 - 27.8 mmol/L]	Regardless of fasting status, consider IV fluids if symptoms of hyperglycemia or signs of volume depletion.
	Exclude confounding factors like e.g. urinary tract infection and consider consultation with a diabetologist.
	Administer intravenous hydration and intervention for electrolyte/ketoacidosis/hyperosmolar disturbances as clinically appropriate. Insulin may be used for 1-2 days until hyperglycemia resolves, however this may not be necessary in the majority of alpelisib-induced hyperglycemia given the short half-life of alpelisib. Start or further intensify oral anti-diabetic treatment and titrate as outlined for Grade 2.
	Monitor blood glucose as clinically indicated and at least twice weekly until blood glucose levels resolve to ≤ Grade 1.
	 If FG resolves to ≤ 160 mg/dL (8.9 mmol/L) within 3-5 days, while off study treatment and on metformin, re-start alpelisib and reduce 1 dose level, continue with anti-diabetic treatment. A second or third anti-diabetic agent maybe initiated concomitantly, if needed, in consultation with a diabetologist. Check blood glucose at least weekly for 8 weeks, then continue checking at least every 2 weeks, alert treating physician if FG>250mg/dl (13.9 mmol/L). If FG does not resolve to ≤ 160 mg/dl (8.9 mmol/L within 3-5 days while off study treatment and on metformin, consult a diabetologist for management of diabetes is strongly recommended. If FG does not resolve to ≤ 160 mg/dL(8.9 mmol/L within 21 days after institution of appropriate anti-diabetic treatment in cooperation with diabetologist and exclusion of confounding factors
	e.g. urinary tract infection, permanently discontinue patient from alpelisib treatment.
Grade 4 FG > 500 mg/dL [> 27.8 mmol/L]	 Omit alpelisib, confirm fasting status of the assessment. If non-fasting, re-check within 24 hours.
	Regardless of fasting status, consider IV fluids

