Worst toxicity – CTCAE Grade (value)	Dose Modifications for alpelisib
	 Exclude confounding factors like e.g. urinary tract infection.
	 Should consult with diabetologist, initiate or intensify medication with appropriate anti-diabetic treatment (see Grade 3), re-check within 24 hours.
	 If grade improves then follow specific grade recommendations
	 If FG is confirmed as > 500 mg/dl (27.8 mmol/L) and confounding factors could be excluded, permanently discontinue patient from alpelisib.

A diabetologist consultation should always be considered

For all grades: instruct patient to follow dietary guidelines according to local and/or institutional standards for management of diabetes mellitus (such as those provided by the American Diabetes Association) during the study, e.g. .small frequent meals, low carbohydrate content, high fiber, balancing carbohydrates over the course of the day; three small meals and 2 small snacks rather than one large meal

In cases where there is rapidly increasing serum glucose suspicious of severe clinical presentation and/or diabetic ketoacidosis) without obvious confounding factors and potentially need close observation and monitoring, a diabetologist should be consulted with consideration of potential hospitalization and close monitoring.

*specific recommendations please see Section 6.3.2.1.3.

Investigations (Hematologic)	
Neutropenia (ANC)	
Grade 1 (ANC < LLN - 1.5 x 10 ⁹ /L)	Maintain dose level
Grade 2 (ANC < 1.5 - 1.0 x 10 ⁹ /L)	
Grade 3 (ANC < 1.0 - 0.5 x 10 ⁹ /L)	Omit dose until resolved to ≤ Grade 1, then:
Grade 4 (ANC < 0.5 x 10 ⁹ /L)	
	 If resolved in ≤ 7 days, then maintain dose level
	If resolved in > 7 days, then ↓ 1 dose level
Febrile neutropenia	Omit dose until resolved, then ↓ 1 dose level
(ANC < 1.0 x 10 ⁹ /L, with a single temperature of ≥	
38.3 °C or a sustained temperature of ≥ 38 °C for more than one hour)	
Thrombocytopenia	
Grade 1 (PLT < LLN - 75 x 10 ⁹ /L)	Maintain dose level
Grade 2 (PLT < 75 - 50 x 10 ⁹ /L)	Walitain dosc level
Grade 3 (PLT < 50-25 x 10 ⁹ /L)	Omit dose until resolved to ≤ Grade 1, then:
	,
	 If resolved in ≤ 7 days, then maintain dose level
	If resolved in > 7 days, then ↓ 1 dose level
Grade 4 (PLT < 25 x 10 ⁹ /L)	Omit dose until resolved to ≤ Grade 1, then ↓ dose
	level
Investigations (Renal)	
Serum creatinine	
<2 x ULN	Maintain dose level
2 – 3 x ULN	Omit dose until resolved to ≤ grade 1, then:

Worst toxicity – CTCAE Grade (value)	Dose Modifications for alpelisib

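### Section 6.3.2.1.3 tells sites to stop all glucose-lowering drugs when alpelisib stops, with no glucose condition, which conflicts with Table 6-3 for patients whose glucose is still uncontrolled

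*Protocol*

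**What the plan says.** The instruction stands in Protocol section 6.3.2.1.3: "Due to the short half-life of alpelisib, all glucose lowering medications should be discontinued when alpelisib is stopped". The only reason given is the half-life. No glucose level, reason for stopping or class of drug is named. The sentence just before it warns about hypoglycemia in patients who interrupt alpelisib while taking insulin or a sulfonylurea.

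Table 6-3 (section 6.3.1.4), which 6.3.2.1.3 names as the place for detailed guidance, handles high glucose as follows.

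- **Grade 3 (FG above 250 to 500 mg/dL).** Alpelisib is omitted and oral anti-diabetic treatment is started or intensified. Insulin may be given for a day or two, until the hyperglycemia has resolved. If FG has not come down to 160 mg/dL or less "within 3-5 days while off study treatment and on metformin, consult a diabetologist for management of diabetes is strongly recommended". If it is still not there "within 21 days after institution of appropriate anti-diabetic treatment in cooperation with diabetologist and exclusion of confounding factors", the action is: "e.g. urinary tract infection, permanently discontinue patient from alpelisib treatment".
- **Grade 4 (FG above 500 mg/dL).** Alpelisib is omitted and the site is told to "initiate or intensify medication with appropriate anti-diabetic treatment (see Grade 3), re-check within 24 hours". Then: "If FG is confirmed as > 500 mg/dl (27.8 mmol/L) and confounding factors could be excluded, permanently discontinue patient from alpelisib".

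On severity, section 6.3.2.1.3 says: "DKA is characterized by ketoacidosis and a comparatively lower hyperglycemic level (blood glucose 250 mg/dL-600 mg/dL"), and it places the hyperosmolar non-ketotic syndrome (HHNKS) above 600 mg/dL.

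**The concern.** Two groups leave alpelisib permanently under Table 6-3 precisely because their glucose is not controlled. The sentence in 6.3.2.1.3 applies at that same moment and says to withdraw every glucose-lowering drug. A site following it to the letter would take treatment away from the patients with the worst control. In the Grade 4 case this would come directly after being told to start or intensify that treatment.

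If 'stopped' is read to include interruption, the conflict is wider. Table 6-3 expects the Grade 3 patient to be taking metformin while alpelisib is held.

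What is at stake is patient safety at discontinuation. The primary endpoint, the secondary efficacy endpoints and the planned analyses are not involved.

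**Working it through.** The plan has no figure on this point to reproduce. The check sets the texts side by side and then tests the stated reason.

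**1. Text against text**

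| Situation | Table 6-3 | Section 6.3.2.1.3 read literally |
|---|---|---|
| Grade 3, alpelisib held | Oral treatment started or intensified; glucose judged on metformin; unresolved cases referred for diabetes management | If 'stopped' includes held: withdraw all |
| Grade 3, permanent stop | FG not 160 mg/dL or less within 21 days of treatment | Withdraw all |
| Grade 4, alpelisib held | Start or intensify treatment, re-check within 24 h | If 'stopped' includes held: withdraw all |
| Grade 4, permanent stop | FG confirmed above 500 mg/dL | Withdraw all |

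The two permanent-stop rows conflict on either reading of 'stopped'. The two held rows conflict only on the wider reading.

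**2. Is there a withdrawal criterion elsewhere?** For insulin, yes: the Grade 3 row ties its use to resolution, and Grade 4 refers back to Grade 3. For metformin, SGLT2 inhibitors, pioglitazone and other oral agents, no end-point is given.

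**3. Does the half-life justify the rule for these patients?**

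Inputs: half-life 8 to 9 h (section 1.2.4.3); the 3 to 5 day checkpoint and the 24 h re-check (Table 6-3). Formula: fraction remaining = 0.5^(t / half-life), assuming first-order elimination from the last dose.

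- Grade 3, 3 days = 72 h: 72/9 = 8.0 to 72/8 = 9.0 half-lives; 0.39% to 0.20% left.
- Grade 3, 5 days = 120 h: 120/9 = 13.3 to 120/8 = 15.0 half-lives; 0.010% to 0.003% left.
- Grade 4, 24 h after a dose taken at detection: 24/9 = 2.7 to 24/8 = 3.0 half-lives; 15.7% to 12.5% left.
- Grade 4, if the last dose was 24 h before detection (48 h in all): 48/9 = 5.3 to 48/8 = 6.0 half-lives; 2.5% to 1.6% left.

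At the Grade 3 checkpoint almost no drug remains. If glucose is still high then, waiting for clearance is unlikely to bring it down, so a short half-life is no reason to withdraw treatment. This step assumes that the glucose effect roughly follows plasma drug; the documents do not establish that. It uses the 3 to 5 day checkpoint and not the 21-day limit, because the 21-day clock runs from the start of anti-diabetic treatment, which may have begun at Grade 1 or 2 while alpelisib continued.

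**4. Glucose levels.** Confirmed FG above 500 mg/dL has no upper bound. It overlaps the upper part (500 to 600) of the 250 to 600 mg/dL range given for ketoacidosis and extends into the HHNKS range above 600.

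**5. How many patients?** The documents do not allow a count for this trial. Section 6.4.1.1 reports that 18 of 284 patients in the phase III trial stopped alpelisib for hyperglycemia: 18/284 = 6.3%, exact 95% CI 3.8% to 9.8%. It does not split them by stopping rule. Looking forward, enrollment was complete by 14-Dec-2020, 9 patients remained on treatment at the count given with Amendment 6, and "Alpelisib induced hyperglycemia typically occurs within the first month of treatment".

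**The case against.** The strongest reply is that the sentence is a hypoglycemia safeguard. It follows a warning about insulin and sulfonylureas, in a section on hyperglycemia caused by alpelisib: once the drug clears, glucose should fall and continued treatment could overshoot. It says 'should', whereas the protocol uses 'must' for mandatory steps. Around it stand clinical judgment (6.3.1.4), local practice (6.3.2.1.3), ADA/EASD guidance (6.4.1.1), diabetologist referral and twice-weekly monitoring (Table 6-3), and mandatory follow-up of adverse events that led to discontinuation until they resolve or stabilize (6.3.2). A diabetologist asked to manage diabetes would not stop every diabetes drug.

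Most of this stands. The likely intent is as described, and a careful site would depart from the literal text. But these are general permissions. None states when oral agents may be withdrawn or exempts the two permanently discontinued groups, so the specific contrary instruction remains.

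Two stronger readings should be resisted. A reader might infer that the protocol gives no withdrawal criterion anywhere; the insulin end-point in Table 6-3 shows otherwise. A reader might also take 'all' to mean that pre-study diabetes therapy must be stopped. Controlled type 2 diabetes is not excluded, so the words reach that far, but the section's subject makes it improbable that this was meant. Entry also requires fasting plasma glucose of 140 mg/dL or less and HbA1c of 6.4% or less, so few patients would be concerned.

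**Conclusion.** The point holds as a minor patient-safety wording conflict. The sentence in 6.3.2.1.3 has no glucose condition, contradicts Table 6-3 if followed literally, and rests on a reason that does not fit patients whose glucose stays high after alpelisib has cleared. The gap concerns oral agents; insulin has an end-point.

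The conflict itself rests on the wording alone. The half-life argument also needs first-order elimination and a glucose effect that roughly tracks drug level.

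The size is small. The number of patients exposed to the conflict cannot be determined. It would be tempting to apply the phase III 6.3% to this trial's enrollment, but that figure covers every discontinuation for hyperglycemia in another trial and says nothing about harm from withdrawing anti-diabetic drugs. Nor do the documents show that any patient here was treated according to the literal sentence. No endpoint or analysis is affected.

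**What to change.** At the next protocol amendment, replace the sentence with:

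> During alpelisib interruption, follow Table 6-3. After permanent discontinuation, continue glucose-lowering drugs started for alpelisib-induced hyperglycemia until FG resolves to Grade 1 or lower (160 mg/dL or less) or baseline, then reduce or stop them according to measured glucose, with particular caution for hypoglycemia with insulin and sulfonylureas. Continue pre-study diabetes therapy as clinically indicated.

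The 160 mg/dL threshold is the upper limit of Grade 1 and the resolution target already used in Table 6-3, so no new standard is introduced, and the hypoglycemia caution is kept.

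The cost is one sentence, which needs a written amendment with IRB/IEC approval (section 12.1). It should be aligned with the Investigator's Brochure and the program's standard language, from which the amendment log says this section was updated. Data collection and analysis do not change.

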6.3.2.1.4 Follow-up on amylase or lipase elevation (≥ CTCAE Grade 3)

Patient with amylase or lipase elevation \geq CTCAE Grade 3 must be tested weekly (or more frequently if clinically indicated) until \leq Grade 1 (or baseline). After resumption of dosing, continue to test weekly for one additional cycle. If no reoccurrence of \geq Grade 2 event, continue monitoring every cycle.

An exception to these follow-up guidelines will be made for cases of isolated amylase elevations in which amylase fractionation demonstrates that pancreatic amylase is \leq Grade 1. In such cases, total amylase and fractionated amylase should be monitored weekly (or more frequently if clinically indicated) for 4 weeks. If pancreatic amylase remains \leq Grade 1, subsequent monitoring must be performed at least every 4 weeks (or more frequently if clinically indicated).

Patients who discontinue study treatment due to pancreatic toxicity must be monitored weekly (or more frequently if clinically indicated) until the event resolves to \leq grade 1 or stabilization occurs (no CTCAE grade change over 4 weeks).

If amylase and/or lipase elevations are accompanied by new or progressive unexplained abdominal symptoms such as severe pain or vomiting, withhold study treatment, then perform diagnostic procedures (e.g., abdominal CT scan or ultrasound) to exclude pancreatic pathology.

See also dose modification guidelines described in Table 6-3.

Note: The R value is calculated by dividing the ALT by the ALP, using multiples of the ULN for both values. It denotes whether the relative pattern of ALT and/or ALP elevation is due to cholestatic ($R \le 2$), hepatocellular ($R \ge 5$), or mixed ($R \ge 2$) liver injury. In clinical situations where it is suspected that ALP elevations are from an extrahepatic source, the GGT can be used if available. GGT may be less specific than ALP as a marker of cholestatic injury, since GGT can also be elevated by enzyme induction or by ethanol consumption. It is more sensitive than ALP for detecting bile duct injury (livertox.nih.gov/rucam.html).

If DILI confirmed: permanently discontinue.

If DILI unlikely - interrupt treatment. Treat identified cause according to institutional guidelines. If resolved, reduce by one dose level. Re-administration of study treatment should be considered only if the investigator assesses benefit to outweigh the risk. Any decision regarding readministration of study drug/s and dose regimen should be discussed with the Novartis medical safety team.

Table 6-5 "Alternative causes of liver disease" provides guidance on specific clinical and diagnostic assessments which can be performed to rule out possible alternative causes of observed Liver Function Tests (LFT) abnormalities.

Table 6-5 Alternative causes of liver disease

Disease	Assessment
Hepatitis A, B, C, E	IgM anti-HAV; HBsAg, IgM anti-HBc, HBV DNA; anti-HCV, HCV RNA, IgM & IgG anti-HEV, HEV RNA

CMV, HSV, EBV infection	IgM & IgG anti-CMV, IgM & IgG anti-HSV; IgM & IgG anti-EBV
Autoimmune hepatitis	ANA & ASMA titers, total IgM, IgG, IgE, IgA
Alcoholic hepatitis	Ethanol history, gammaGT, MCV, CD-transferrin
Nonalcoholic steatohepatitis	Ultrasound or MRI
Hypoxic/ischemic hepatopathy	Medical history: acute or chronic CHF, hypotension, hypoxia, hepatic venous occlusion. Ultrasound or MRI.
Biliary tract disease	Ultrasound or MRI, ERCP as appropriate.
Wilson disease	Caeruloplasmin
Hemochromatosis	Ferritin, transferrin
Alpha-1-antitrypsin deficiency	Alpha-1-antitrypsin

Following appropriate causality assessments, as outlined above, the causality of the drug is estimated as "probable" i.e. > 50% likely, if it appears greater than all other causes combined. The term "drug-induced" indicates probably caused by the drug, not by something else, and only such a case can be considered a DILI case and should be reported as an SAE.

6.3.2.3 Guidelines for hypersensitivity

Alpelisib and combination drug are associated with hypersensitivity reactions, including anaphylaxis and angioedema. These are manifested by symptoms including, but not limited to, dyspnea, flushing, rash, fever, hypotension, dizziness, tachycardiaand facial or laryngeal oedema. Alpelisib and/or combination drug should be permanently discontinued and should not be re-introduced in participants with serious hypersensitivity reactions. Appropriate treatment should be promptly initiated.

6.3.3 Anticipated risks and safety concerns of the study drug

Appropriate eligibility criteria, as well as specific dose modification and stopping rules are included in this protocol (see Section 6.3 for details).

6.4 Concomitant medications

6.4.1 Permitted concomitant therapy

Medications required to treat adverse events, manage cancer symptoms, concurrent diseases and supportive care agents, such as pain medications, anti-emetics and anti-diarrheal are allowed, except if specifically prohibited (see Section 14, Appendix 1).

All medications (other than study drug) and significant non-drug therapies (including vitamins, physical therapy, and blood transfusions) administered within 30 days prior to the start of study treatment and up to 30 days after the last dose of study treatment must be recorded on the Concomitant Medications or the Surgical and Medical Procedures eCRF (Core Phase only).

The investigator should instruct the participant to notify the study site about any new medications and/or non-drug therapies/procedures he/she takes after signing the informed consent. Each concomitant drug must be individually assessed against all exclusion criteria/prohibited medication. If in doubt, the investigator should contact the Novartis medical monitor before randomizing a participant or allowing a new medication to be started. If the

11010001110: 0512713/12402

participant is already enrolled, contact Novartis to determine if the participant should continue participation in the study.

6.4.1.1 Oral anti-diabetics

Patients who develop hyperglycemia during the study should be treated according to the ADA (American Diabetes Association) guidance and/or European Association for the study of Diabetes (EASD).

Consultation with a diabetologist or healthcare provider experienced in the management of hyperglycemia is highly recommended for better assessment and management of alpelisib-induced hyperglycemia. It is recommended to start treatment with metformin, however sodium-glucose cotransporter 2 (SGLT2) inhibitors as per standard practices/standard of care, may be a suitable alternative or add-on therapy to metformin. SGLT2 inhibitors are a class of diabetic medications that improve hyperglycemia primarily by promoting urinary glucose excretion.

In the SOLAR-1 study, among the 284 participants who were randomized to receive alpelisib plus fulvestrant, 190 participants (67%) developed hyperglycemia, with 18 patients (6%) discontinuing alpelisib treatment due to hyperglycemia, as of 30-Sep-2019.

Among those with hyperglycemia, 166 participants received concomitant anti-diabetic medications, primarily consisting of metformin (87%). However, in addition to metformin, 6 participants also received an SGLT2 inhibitor, consisting of empagliflozin, ipragliflozin, or dapagliflozin. All 6 participants had ≥ 1 risk factor at baseline for developing hyperglycemia, defined as prediabetes (n = 4; 1 of whom had documented history of type 2 diabetes), diabetes (n = 2), and obesity (n = 2). The most severe hyperglycemia in these participants was grade (G) 3 (n = 5). After initiating an SGLT2 inhibitor, all subsequent hyperglycemia events were G 1/2, except one G 3 event with steroids as a confounding factor. The duration of alpelisib ranged from 9.5 to 27.7 months in these 4 participants who discontinued alpelisib; and notably, 2 participants were continuing to receive alpelisib after 37.0 and 40.0 months, respectively. None of the 6 participants discontinued alpelisib due to hyperglycemia.

Participants with at least one risk factor for the development of severe hyperglycemia, defined as prediabetes/diabetes, and/or obesity (BMI \geq 30), and/or age \geq 75 years, may benefit from the initiation of an SGLT2 inhibitor with metformin, which is available as a single oral combination pill or as two separate medications. The decision to initiate an SGLT2 inhibitor alone in combination with metformin is at the discretion of the investigator. For more details on metformin XR, please refer to Table 6-3.

.

